12.1.2 Serious Adverse Event (SAE)

An adverse event is considered a SAE if it:

- Led to death
- Led to a serious deterioration in the health of the subject, that either resulted in:
 - a) A life-threatening illness or injury, or
 - b) A permanent impairment of a body structure or a body function, or
 - c) In-patient hospitalization, or prolongation of existing hospitalization, or

- d) medical or surgical intervention to prevent permanent life-threatening illness or injury or permanent impairment to body structure or a body function.
- Led to fetal distress, fetal death or a congenital abnormality

Planned hospitalization for a pre-existing condition, without serious deterioration in health, is not considered a serious adverse event.

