12.1.3 Serious Adverse Device Effect (SADE)

A serious adverse device effect is defined as an adverse event related to the use of an investigational medical device that has resulted in any of the consequences characteristic of a serious adverse event.

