12.2 Adverse Event Reporting

Any adverse event that occurs during the course of the study must be reported using the Adverse Event (AE) Form in the CRFs and the Investigator must sign each report. The Investigator must determine whether the adverse event is serious or unanticipated, its intensity, and the relationship of each adverse event to the investigational device or procedure.

Pre-existing medical conditions or symptoms occurring prior to the laparoscopic procedure involving the MSS should not be reported as adverse events, unless there is a worsening of the pre-existing medical condition.

All serious adverse events, including unanticipated serious adverse device effects, must be reported to the Sponsor within 24 hours of the site first becoming aware of the event via email ([contact]). At a minimum, the AE CRF should be provisionally completed, scanned and sent via email. The Sponsor will contact the site for additional information, if required.

For any adverse event that is ongoing at the time of the initial report, periodic follow-up information is required until the adverse event is resolved or is not expected to change. The site should submit relevant follow-up information related to the adverse event as soon as it is available.

Depending upon the nature and seriousness of the adverse event, the Sponsor may request the Investigator to provide copies of the subject's medical records (such as the subject's laboratory tests and hospital records, Investigator summaries, etc.) to document the adverse event. The Sponsor is

available to respond to any medical issues that arise during the conduct of this study.

The Investigator will report all serious adverse events, including unanticipated serious adverse device effects, to the EC according to the EC requirements. A copy of this EC communication should be sent to the Sponsor.

The Sponsor will ensure that safety reporting for the study is conducted in compliance with all pertinent requirements and regulations.

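### SAE item (d) in 12.1.2 covers an averted life threat only if the threat would have been permanent; item (a) has no such condition, so a narrow class of treated events can be classed as non-serious

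*Combined protocol and SAP*

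**What the plan says.** Section 12.1.2 makes an event serious if it led to death, to specified fetal or congenital harm, or to a serious deterioration in health with one of four results. The lead-in to those four is "Led to a serious deterioration in the health of the subject, that either resulted in".

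- Item (a): "A life-threatening illness or injury, or".
- Item (b): permanent impairment of structure or function.
- Item (c): "In-patient hospitalization, or prolongation of existing hospitalization, or".
- Item (d): "medical or surgical intervention to prevent permanent life-threatening illness or injury or permanent impairment" of structure or function.

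Other sections depend on this definition. Section 12.1.3 defines a serious adverse device effect (SADE) as a device-related event that "has resulted in any of the consequences characteristic of a serious adverse event". Section 12.1.4 defines the unanticipated form (USADE) as a kind of SADE. Under 12.2, serious events "must be reported to the Sponsor within 24 hours of the site first becoming aware of the event", and the investigator also reports them to the ethics committee (EC). Section 12.2 leaves the judgement of seriousness to the investigator. Section 5.1 makes seriousness one of the axes on which adverse events are summarised.

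**The concern.** Items (a) and (b) cover harm that happened: a life threat, or a permanent impairment. Item (d) covers the same two harms where treatment prevented them. Its impairment limb matches (b), because both are limited to permanent impairment. Its life-threat limb does not match (a), because (d) adds *permanent* and (a) does not. The Life-Threatening severity grade in 12.3 has no permanence condition either.

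Risk to life is ordinarily acute: it is either realised or removed. An investigator who applies (d) as written would find very few averted life threats that qualify.

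The events concerned matter in this study. Section 8.2 lists bleeding, vascular injury, gastro-intestinal injury and organ perforation among the risks, and any of these can be treated during the operation. Seriousness is what triggers prompt notice to the sponsor and the EC. Severity grading in 12.3 carries no reporting clock. Section 12.6 on device deficiencies states no time limit. Monitoring visits are optional under 8.3 and 11.2. Section 13.9 also lists late SAE reporting as a possible reason to suspend a site, so sites need a definition that they can apply in only one way.

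**Working it through.** The plan states no SAE rate, so there is no figure of its own to reproduce. The check is to take an intra-operative injury that was treated at once and follow it through 12.1.2. Every row assumes that the lead-in (serious deterioration) is met.

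| Case | Route | Serious as written? | Serious with the first *permanent* deleted? |
|---|---|---|---|
| 1. Life was at risk, however briefly, before control | (a) | Yes | Yes |
| 2. Controlled before life was at risk, but stay prolonged | (c) | Yes | Yes |
| 3. Controlled before life was at risk; repair prevented permanent impairment | (d), second limb | Yes | Yes |
| 4. Controlled before life was at risk; stay not prolonged; no permanent impairment threatened; treatment averted a life threat | (d), first limb only | No, read literally | Yes |

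Only case 4 turns on the disputed word. If the lead-in is not met, none of (a) to (d) applies and the deletion changes nothing.

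**What follows in case 4.** A non-serious event cannot be a SADE (12.1.3), so it cannot be a USADE (12.1.4). Neither the 24-hour sponsor report nor the EC report in 12.2 is triggered. The event still goes on the AE form, because 12.1.1 requires every adverse event to be recorded. It appears in the 5.1 summary, but as non-serious.

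**Illustration of size.** The inputs are n = 100 (the target maximum in 6.2 and the planned size in 9.2) and x reclassified subjects. The value of x is an assumption. Take x from 0 to 3, with no other serious events. Each reclassified subject moves the rate by 1/100, or 1 percentage point. The exact (Clopper-Pearson) 95% limits at the two ends are:

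- x = 0: the lower limit is 0; the upper limit is 1 − 0.025^(1/100) = 0.036. Result: 0/100, 0 to 3.6%.
- x = 3: the lower limit is the 2.5% quantile of Beta(3, 98) = 0.006; the upper limit is the 97.5% quantile of Beta(4, 97) = 0.085. Result: 3/100, 0.6 to 8.5%.

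**The case against.** A reader might infer that any intra-operative bleed repaired at once is non-serious under this plan and escapes the 24-hour report. The documents do not support that. Item (a) sets no minimum duration, so a bleed that put the subject at risk of death is serious even if it was controlled in minutes. Successful treatment does not undo a threat that existed. Nor does full recovery take a repair outside (d): preventing permanent impairment is what its second limb describes, and repair of a vessel or an organ will often fit it. A prolonged stay qualifies under (c). These objections stand, and they reduce the point to case 4.

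It can also be said that the deletion may not rescue case 4, because an injury controlled at once may not amount to a serious deterioration. That stands in part. The change helps only events that pass the lead-in, and how many do is not known.

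Other provisions soften the effect. Case 4 events remain on the AE form, may well be graded Severe under 12.3 because they needed treatment, and are evaluated by the sponsor under 13.10. So they are not lost. None of these provisions supplies the 24-hour clock or the EC report.

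Finally, an investigator may read *permanent* loosely and report the event anyway. That is possible, but it means that classification depends on the reader, at up to five sites (6.2), which is itself a reason to settle the wording.

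**Conclusion.** The point holds in a narrow form. Item (d) does not match item (a), and on a literal reading its averted-life-threat limb has almost no content. The likely result is that a small residual class of events is classed as non-serious, or classed inconsistently between sites. The documents do not show that serious injuries in general would go unreported.

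The number affected is unknown and may be zero, because the documents give no event rate. The change from 0/100 to 3/100 only illustrates how visible a few reclassified events would be in a study of this size. It assumes 100 treated subjects, no other serious events, and that all three meet the lead-in and fall in case 4. Section 9.1 plans descriptive output only, so no test or threshold turns on the difference. The practical weight lies in prompt notice to the sponsor and the EC. The change is worth making because it is specific, nearly free and protects subjects.

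**What to change.** In 12.1.2 item (d), delete the first *permanent*, the one before the life-threat phrase. Keep the second, which limits the impairment limb and matches item (b). Leave the lead-in and items (a) to (c) unchanged. Make the seriousness categories on the AE CRF and any completion guidance match. SADE, USADE and the 12.2 reporting duties then follow without further edits.

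The cost is one word in the protocol, a matching check of the CRF, and approval through the amendment process in 13.4. The downside is possibly a few more events reported within 24 hours.

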12.1.3 Serious Adverse Device Effect (SADE)

A serious adverse device effect is defined as an adverse event related to the use of an investigational medical device that has resulted in any of the consequences characteristic of a serious adverse event.

12.1.4 Unanticipated Serious Adverse Device Effect (USADE)

An USADE is a serious adverse device effect which by its nature, incidence, severity or outcome has not been identified in the current version of the investigational plan.

12.2 Adverse Event Reporting

Any adverse event that occurs during the course of the study must be reported using the Adverse Event (AE) Form in the CRFs and the Investigator must sign each report. The Investigator must determine whether the adverse event is serious or unanticipated, its intensity, and the relationship of each adverse event to the investigational device or procedure.

Pre-existing medical conditions or symptoms occurring prior to the laparoscopic procedure involving the MSS should not be reported as adverse events, unless there is a worsening of the pre-existing medical condition.

All serious adverse events, including unanticipated serious adverse device effects, must be reported to the Sponsor within 24 hours of the site first becoming aware of the event via email ([contact]). At a minimum, the AE CRF should be provisionally completed, scanned and sent via email. The Sponsor will contact the site for additional information, if required.

For any adverse event that is ongoing at the time of the initial report, periodic follow-up information is required until the adverse event is resolved or is not expected to change. The site should submit relevant follow-up information related to the adverse event as soon as it is available.

Depending upon the nature and seriousness of the adverse event, the Sponsor may request the Investigator to provide copies of the subject's medical records (such as the subject's laboratory tests and hospital records, Investigator summaries, etc.) to document the adverse event. The Sponsor is

available to respond to any medical issues that arise during the conduct of this study.

The Investigator will report all serious adverse events, including unanticipated serious adverse device effects, to the EC according to the EC requirements. A copy of this EC communication should be sent to the Sponsor.

The Sponsor will ensure that safety reporting for the study is conducted in compliance with all pertinent requirements and regulations.

12.3 Adverse Event Severity

The Investigator must determine the severity of the adverse event according to the following definitions:

Mild The adverse event is noticeable to the subject, but does not interfere with routine activity; the symptoms are easily tolerated and transient in nature.

Moderate The adverse event interferes with routine activity but responds to symptomatic therapy or rest; the symptoms are poorly tolerated and sustained.

Severe The adverse event significantly limits the subject's ability to perform routine activities despite symptomatic therapy. The adverse event requires medical or surgical treatment or results in hospitalization.

Life-Threatening The subject is at immediate risk of death.

12.4 Event Relationship

The following lists the potential event attribution categories.

12.4.1 Device Related

An adverse event is considered device-related when the clinical event has a reasonable time sequence associated with use of the investigational device and is unlikely to be attributed to concurrent disease or other procedures or medications. It is reasonable to believe that the device directly caused or contributed to the adverse event.

The Investigator will evaluate the relationship of the adverse event to the MSS and/or LRP according to the following definitions:

Definite The adverse event is clearly related to the investigational device: the event has a temporal relationship to the investigational device, follows a known pattern of response, or is otherwise logically related to the investigational device, and no alternative cause is present.

Probable The adverse event is likely related to the investigational device: the event has a temporal relationship to the investigational device, follows a known or suspected pattern of response, or is otherwise logically related to the investigational device, but an alternative cause may be present.

Not likely The adverse event is unlikely related to the investigational device: the event does not follow a clear temporal relationship to the investigational device or does not follow a known pattern of response, or is otherwise likely to be due to the subject's clinical state or other modes of therapy.

Not related The adverse event is clearly not related to the investigational device: the event has no temporal or other relationship to the administration of the investigational device, follows no known or suspected pattern of response, and an alternative cause is present.

Unknown Unable to determine the relationship based on all available information.

12.4.2 Procedure-Related

An adverse event is considered to be procedure-related when it is reasonable to believe that the event is associated with the index procedure and is not specific to the investigational device. Other products, surgical techniques, or medications required specifically for the procedure may have contributed to the occurrence of the event.

The Investigator will evaluate the relationship of the adverse event to the procedure according to the following definitions:

Definite The adverse event is clearly related to the procedure: the event has a temporal relationship to the procedure, follows a known pattern of response, or is otherwise logically related to the procedure, and no alternative cause is present.

Probable The adverse event is likely related to the procedure: the event has a temporal relationship to the procedure, follows a known or suspected pattern of response, or is otherwise logically related to the procedure, but an alternative cause may be present.

Not likely The adverse event is unlikely related to the procedure: the event does not follow a clear temporal relationship to the procedure or does not follow a known pattern of response, or is otherwise likely to be

due to the subject's clinical state or other modes of therapy.

Not related The adverse event is clearly not related to the procedure: the event has no temporal or other relationship to the procedure, follows no known or suspected pattern of response, and an alternative cause is present.

Unknown Unable to determine the relationship based on all available information.

12.5 Subject Death

Any subject death during the investigation must be reported to Levita Magnetics within 24 hours of Investigator's knowledge of the death. The Adverse Event CRF must be completed and include a complete description of the relevant details of the death. A copy of the death records, death certificates and an autopsy report (if performed) are required to be sent to the Sponsor. In addition, subject death must be reported to the EC in accordance with EC requirements.

12.6 Device Deficiency

All device deficiencies related to the identity, quality, durability, reliability, safety or performance (includes malfunctions, use errors, and inadequate labeling) of the device shall be documented. Sponsor will assess all device deficiencies that could have led to a serious adverse device effect.

In the event of a suspected malfunction or device deficiency, the investigational device should be returned to the Sponsor for analysis. Instructions for returning the investigational device will be provided by the Sponsor.

13 STUDY ADMINISTRATION

13.1 Statement of Compliance

The clinical investigations will be in accordance with the ethical principles of the Declaration of Helsinki (59th WMA General Assembly, Seoul, October 2008) and ICH-GCP Guidelines. The clinical investigation shall not commence until approval by the EC. Any additional requirements imposed by the EC or regulatory authority shall be followed. The Sponsor shall maintain a Clinical Trial Liability Policy with an insurance company.

13.2 Ethics Committee (EC) Approval

The study protocol shall be reviewed and approved by the Investigator's EC prior to subject enrollment. All proposed changes to the investigational plan

must be reviewed and approved by the Sponsor in writing prior to implementation. Significant changes to the investigational plan must be approved in writing by the Sponsor and the EC prior to implementation. A significant change is one which may increase the risk or present a new risk to a subject, or which may adversely affect the scientific validity of the study.

Prior to allowance of study enrollment, a signed copy of the EC approval letter identifying the clinical study and investigational site is required to be submitted to the Sponsor. Investigators are responsible for obtaining and maintaining annual renewal of the study by their EC (or according to renewal schedule imposed by the EC). Evidence of renewal and continued EC approval must be provided to the Sponsor accordingly.

13.3 Informed Consent

Written informed consent is mandatory and must be obtained from all subjects as per local regulations, prior to their participation in the study. A template Informed Consent is provided in Appendix 1.

It is the responsibility of the Investigator to ensure written informed consent from each subject is obtained prior to the initiation of any study-related procedures.

Study participation is voluntary, and refusal to participate will involve no penalty or loss of benefits to which the subject is otherwise entitled.

Study personnel fully knowledgeable in the purposes and procedures of the study will approach all prospective study participants. The facilities and settings in which prospective participants will be presented with the opportunity to learn about and consent to participation in the study will provide them sufficient quiet and unhurried time to be informed of the study and to ask questions prior to the initiation of study procedures. Study personnel will, after presenting the study to prospective participants, assess the subject's understanding and autonomy by asking the subject to explain the study in his/her own words.

Once that step is completed, consent will be able to be given by the subject signing the consent form. A copy of the consent form will be given to all consented participants.

Signed subject consent forms must be retained in the study files by the Investigator, and be available for review by the Sponsor and/or regulatory agencies, as applicable.

The informed consent form and any other written information provided to subjects will be revised whenever important new information becomes available, or if there is an amendment to the protocol which necessitates a

change to the content of subject information and/or to the consent form. The Investigator will inform the subject of changes in a timely manner, and will ask the subject to confirm his/her continuation in the study by signing a revised consent form.

Any revised informed consent form and other written information provided to subjects must receive approval from the EC and Sponsor prior to use.

13.4 Amending the Protocol

This protocol is to be followed exactly, and will only be altered by written amendments. Amendments must be approved by all parties responsible for approving the protocol prior to implementation. The Informed Consent and CRFs will be reviewed to ensure these are amended if necessary.

Administrative changes that do not affect the benefit/risk ratio or scientific validity of the study (e.g., editorial changes for clarity) may be made with just approval from the Sponsor and will be documented as a protocol revision.

13.5 Protocol Deviations/Violations and Medical Emergencies

A protocol deviation or violation is a failure to comply with the requirements of the clinical study as specified in the protocol. Examples of protocol deviations include late visits, missed visits, and required follow-up testing not completed. An example of a protocol violation includes enrollment of a study subject who fails to meet inclusion/exclusion criteria as specified in the protocol or failure to obtain informed consent. Each Investigator shall conduct this clinical study in accordance with the study protocol and any conditions required by the reviewing EC.

Deviations/violations from clinical protocol requirements will be reviewed and evaluated on an ongoing basis and, as necessary, appropriate corrective actions put into place. Levita Magnetics accepts the right of the Investigator to deviate from the protocol in an emergency when necessary to safeguard the life or the physical well-being of a study subject but such deviation must be reported within **24 hours** of implementation to the EC and Sponsor.

13.6 Pre-Study Documentation Requirements

Prior to shipment of investigational product, the following documents must be provided to Levita Magnetics:

- Signed protocol/protocol amendments
- Signed and dated Investigator Agreement(s)
- A copy of the written EC approval of the protocol
- A copy of the written EC approval of the Informed Consent Form
- Signed and dated Curriculum Vitae of the Investigator(s)
- Copy of the Investigator(s)' current medical license(s), or equivalent
- Signed and dated Financial Disclosure Form(s)

